6.6.3. Biomarker Assessments

6.6.3.1 HIV-antibody Test. HIV-negative and status unknown participants will receive a fingerstick DBS test at 3-month intervals, as recommended by the CDC for high-risk individuals. Participants who show documentation of HIV-positive serostatus are not given a HIV-antibody test. If the test is reactive, then the participant will be presumed positive for HIV antibodies and referred for additional evaluation and treatment. If the DBS sample is rejected by the lab or if the quantity of blood is insufficient, participants will be asked to come to the study site to have the test performed via fingerstick blood test using the INSTI HIV 1/HIV 2 antibody test, or to provide a copy of recent results (within 3 months) from their medical provider. Conducted at baseline and at the 3-, 6-, and 9-month follow-up time points (if previously tested HIV-negative or status is unknown).

6.6.3.2 STI Testing. Participants will be tested for urinary N. gonorrhoea and Chlamydia, pharyngeal and rectal swabs will be taken for N. gonorrhoea and Chlamydia, and syphilis will be tested by fingerstick DBS. Positive STI results will be reported per state guidelines and will be immediately referred to care. If the DBS sample is rejected by the lab or if the quantity of blood is insufficient, participants will be asked to come to the study site to have the test performed via intravenous blood draw or to provide a copy of recent results (within 3 months) from their medical provider. Conducted at baseline and at the 3-, 6-, and 9-month follow-up time points.

6.6.3.3 Virologic Control for HIV-positive Participants. As indicated by an undetectable HIV-1 level via intravenous blood draw, which has a threshold for undetectability = <30 copies/mL will be performed by Foundation Laboratory. Viral load testing through Foundation Laboratory may be bypassed if participants can provide recent (within 3 months) lab results from their medical provider. Conducted at baseline and at the 3-, 6-, and 9-month follow-up time points.

6.6.3.4 Dried Blood Spot (DBS) for HIV-negative Participants who Report PrEP Uptake. A blood sample will be collected and a DBS analysis for intra-erythrocytic TFV-DP will be performed by Molecular Testing Labs. Conducted at baseline and at the 3-, 6-, and 9-month follow-up time points.

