8.2 Advancement through the HIV Prevention or Care Continuum

Advancement through the HIV Prevention or Care Continuum will be assessed at all time points throughout the study, and will be operationalized dichotomously (i.e., yes/no achievement of one of the steps on either the HIV Prevention or Care Continuum; e.g., viral suppression), and

as a counted variable (e.g., consecutive DBS results indicating successful PrEP adherence). Power calculations related to advancement through either continuum will assume a 30% probability of achievement of at least one of the steps on either the HIV Prevention or Care Continuum (equivalent to ~1:2 odds of advancement). Methamphetamine use outcomes will be assessed repeatedly (i.e., at all time points) and will be operationalized dichotomously (e.g., methamphetamine-metabolite-free urine sample), as a counted variable (i.e., number of methamphetamine-metabolite-free urine samples provided), and as a continuous variable (i.e., Treatment Effectiveness Score [total number of methamphetamine-metabolite-free sample divided by total samples possible]). Power calculations related to methamphetamine use outcomes assume an 80% probability of methamphetamine use during the pre-intervention period for participants in the DD arm (equivalent to 4:1 odds of use).

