8.3 HIV Sexual Risk Behavior

HIV sexual risk behavior outcomes will be assessed at all time points throughout the study, and will be operationalized dichotomously (e.g., incident STI via biomarker testing), as a counted variable (e.g., number of days/times engaged in CAI in the past 30 days), and as a continuous variable (e.g., a HIV risk severity index generated from multiple factor-analyzed items). Power calculations for engagement in HIV sexual risk behaviors assume a 65% probability of engagement during the pre-intervention period for participants in the DD arm (equivalent to ~2:1 odds of engagement). Multivariable inferential analyses of dichotomous outcomes will take the form of GLMs employing the Bernoulli family and logit link function; counted outcomes will be analyzed with GLMs employing the Poisson-log or negative binomial link functions as distributional patterns dictate (note: if data evidence an over-representation of zeros or an overdispersion of variance, zero-inflated Poisson and/or negative binomial analyses may be substituted); continuous outcomes will be analyzed using GLMs employing the identity link and Gaussian family functions and assume a single covariate unless otherwise stated (note: iteratively reweighted, bootstrapped, or jack-knifed estimation procedures may be used in Gaussian models if sensitivity analyses indicate undue influence from outliers). Mixed effects GLM models are considered the best linear unbiased estimators for repeated measures data employing non-parametric and/or limited dependent variables. All power calculations are premised on tests of association across two time points (e.g., baseline with app completion; app completion with brick-and-mortar program completion), providing the most conservative estimate of minimum detectable effect (MDE) size estimations; all power calculations assume $\alpha \leq 0.05$ (two-tailed), and $1 - \beta = 0.80$.

Table 2: Instruments, Targets, Variable Operationalizations, and Minimum Detectable Effects

Table 2: Instruments, Targets, Variable Operationalizations, and Minimum Detectable Effects (1 - β = 0.80; α = 0.05, two-tailed)

Instrument	Target	Variable Operationalizations			Power-- Minimum Detectable Effects		
		Dichotomous (Di)	Count (Cu)	Continuous (Co)	Model 1— RCT (Aim 1a; n=150/n=150)	Model 2— Tx Effects (Aim 1b; N = 300)	Model 3— Matched Comparison (Aim 1c; N = 300/N ~ 600)

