DSM-5 (MA)	Diagnosis of MA Use Disorder	Presence/Absence of MA Use Disorder	# of Diagnostic Criteria Endorsed	N/A	Potential Statistical Controls; Exploratory Sub-Group Analyses		
URICA	Stage of Change/ Readiness for Change	Above/Below "Action" Stage	N/A	URICA Score(s)	Potential Statistical Controls; Exploratory Sub-Group Analyses		
Admissions & Follow-up Form	Sociodemographics; HIV Status and Tx History, Barriers & Facilitators	Sexual Identity; HIV Status; Linked/Unlinked; Housing Insecurity	Prior Drug Treatment Episodes; Symptomology	Age; Income	Potential Statistical Controls; HIV-Related Sub-Group Analyses; Barrier/Facilitator Moderator Analyses		
	HIV Prevention or Care Continuum ^a	HIV Test; PrEP Uptake; Advance along HIV Prevention or Care Continuum	Prevention or Care Continua Steps Completed	N/A	Di: OR = 1.97; Cu: IRR = 1.51; Co: f^2 = 0.03	Di: OR = 1.61; Cu: IRR = 1.35	Di: OR = 1.52; Cu: IRR = 1.30; Co: f^2 = 0.01
Biomarker Tests (UA, VL, DBS, HIV/STI)	MA Use, HIV Prevention/Care Continuum Outcomes, Sexual Risk Behavior	Incident STI /Incident HIV	Log reductions in HIV VL; DBS Analysis of PrEP	Treatment Effectiveness Score	Variable	Variable	Variable
Substance Use Freq.	MA Use	Use/Non-use	Days of Use	N/A	Di: OR = 0.48; Cu: IRR = 0.85; Co: f^2 = 0.03	Di: OR = 0.59; Cu: IRR = 0.89; Co: f^2 = 0.01	Di: OR = 0.62; Cu: IRR = 0.90; Co: f^2 = 0.01
BQA	HIV Sexual Risk Behavior	CAI ^b	# CAI ^b Episodes	HIV Sexual Risk Scale	Di: OR = 0.52; Cu: IRR = 0.78; Co: f^2 = 0.03	Di: OR = 0.63; Cu: IRR = 0.85; Co: f^2 = 0.01	Di: OR = 0.66; Cu: IRR = 0.87; Co: f^2 = 0.01
Locator	Contact Information						

^aHIV Prevention Continuum (HIV testing and PrEP/PEP uptake) and HIV Care Continuum (link, ART adherence, virological suppression).

^bCAI: Condomless Anal Intercourse includes both receptive and insertive anal intercourse, and will be assessed by partner type (e.g., main, casual, exchange)

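### Table 2 lists log reduction in HIV viral load as a count, so section 8.3 sends a signed, fractional variable to Poisson or negative binomial models

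*Combined protocol and SAP*

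**What the plan says.** Table 2 (in section 8.3) gives each instrument a dichotomous, a count and a continuous form, in that order, followed by three columns of minimum detectable effects. In the biomarker row the count form is "Log reductions in HIV VL; DBS Analysis of PrEP" and the continuous form is the Treatment Effectiveness Score. The three effect cells of that row carry only the word Variable, with no figure.

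Section 8.3 then fixes the model by type of variable. For counts: "counted outcomes will be analyzed with GLMs employing the Poisson-log or negative binomial link functions as distributional patterns dictate". If there are too many zeros or too much variance, "zero-inflated Poisson and/or negative binomial analyses may be substituted". For the continuous form: "continuous outcomes will be analyzed using GLMs employing the identity link and Gaussian family functions".

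Section 6.6.3.3 says that viral load is taken by blood draw in HIV-positive participants, with a "threshold for undetectability = <30 copies/mL". It is scheduled at baseline and months 3, 6 and 9, and a recent result from the participant's own provider may replace the study test. Section 8.2 uses viral load in another form, as viral suppression yes or no.

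**The concern.** The column decides the model. Poisson and negative binomial distributions put probability only on 0, 1, 2 and so on. A log change takes any real value and falls below zero whenever viral load goes up. An analyst who follows Table 2 and section 8.3 literally would therefore apply a family that does not describe the variable.

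What is at stake is the validity of one biomarker result, and an unplanned choice about how to handle rises in viral load, made after the data are seen.

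**Working it through.** **1. Is the placement real, or an effect of text extraction?** The biomarker row has eight fields, as many as Table 2 has columns. The fourth holds the viral-load entry. The fifth is the Treatment Effectiveness Score, which section 8.2 describes "as a continuous variable (i.e., Treatment Effectiveness Score". The fifth field is therefore the Continuous column and the fourth is the Count column.

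**2. Is there a count definition elsewhere?** None was found. Section 8.2 gives a genuine count for the other entry in the same cell (a run of consecutive dried blood spot results showing PrEP adherence). For viral load it names only suppression, which is dichotomous.

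**3. What values can the variable take?** Reduction = log10(baseline / follow-up). The viral loads below are assumed for illustration:

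| Baseline | Follow-up | log10 reduction |
|---|---|---|
| 10,000 | 30 | 2.523 |
| 5,000 | 400 | 1.097 |
| 30 | 30 | 0 |
| 30 | 200 | -0.824 |
| 400 | 5,000 | -1.097 |

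The Poisson log-probability with mean 1, evaluated at -0.52 and at 1.1, is minus infinity in both cases. At 2 it is -1.693. Only non-negative integers have support.

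**4. What does a count model then do?**
- *Log link.* The fitted mean is exp(linear predictor), which is above zero. A group whose viral load rises on average cannot be represented.
- *Log base.* Natural-log values are log10 values times ln 10 = 2.303. Multiplying the outcome by a constant shifts the intercept and leaves the group coefficient unchanged. The model-based Poisson variance is proportional to 1/mean, so the standard error is multiplied by 1/√2.303 = 0.659. The same data give a different p-value according to the base, which the plan does not state.
- *Software.* On 100 simulated normal values (mean 0.3, SD 1; 34 negative, none an integer), standard routines returned Poisson and negative binomial coefficients, with convergence warnings in the run. The misfit need not show itself as a failed fit.

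**5. What if rises are dropped or set to zero?** Assume normal log10 reductions with SD 1, mean 0.3 in one arm and 0.0 in the other. With mean m, dropping negatives gives m + φ(m)/Φ(m). Setting them to zero gives mΦ(m) + φ(m).

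| | m = 0.3 | m = 0.0 | Difference |
|---|---|---|---|
| True | 0.300 | 0.000 | 0.30 |
| Negatives dropped | 0.3 + 0.3814/0.6179 = 0.917 | 0.3989/0.5 = 0.798 | 0.12 |
| Negatives set to zero | 0.3 × 0.6179 + 0.3814 = 0.567 | 0.399 | 0.17 |

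Each within-group mean is overstated, while the between-arm difference shrinks.

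**6. Which contrasts are touched?** The delayed arm receives the app at 30 days (section 3.1), so both arms have had access by the first follow-up viral load at month 3. The Aim 1b pairing in section 9.2 uses enrolment, month 1 and month 2 data, and no viral load is scheduled at months 1 or 2.

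**7. Power after the move (context only).** With one covariate, two-sided alpha 0.05 and power 0.80, a noncentral F calculation gives a minimum detectable f² of 0.026 at N = 300, which rounds to the 0.03 that Table 2 shows for Aim 1a. The number of HIV-positive participants is not given. Over an assumed range, f² is 0.040 at N = 200, 0.053 at N = 150 and 0.080 at N = 100.

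**The case against.** The best defence is that the cell is shorthand. The plural could mean a number of whole-log drops, which would be a count, and its neighbour in the cell is just as terse yet has a count reading in section 8.2. But no such definition is given for viral load, and whole-log drops would discard fractional change and rebounds. The clause about distributional patterns does not help either: it chooses among count models. The statement in section 8.1 about tests chosen by distribution concerns the screening of covariates, not the outcome models.

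Other parts of the defence stand. A reader might infer that the analysis cannot be run, or that participants with rises will be lost. The documents describe no dropping or rounding, and software may return estimates. A reader might also infer a bias towards benefit. That holds for a within-group mean if rises are dropped or zeroed; for the randomised comparison the illustration goes the other way. Nor are values below 30 copies/mL undefined: the threshold is a detection limit, so changes that involve such values are censored. Finally, the timing of the measurements leaves this variable little part in the month-1 randomised comparison or the Aim 1b pairing, and the viral-suppression outcome is unaffected.

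**Conclusion.** The point holds as a mismatch between variable and model: Table 2 and section 8.3 together assign a count family to a variable that is fractional and can be negative. That follows from the nature of a log change; the documents do not say it themselves. Whether the result would be a failed fit or a misleading one depends on software and analyst, and the share of participants with rises is not given, so no trial-specific bias can be quantified. The differences of 0.12 and 0.17 against a true 0.30 rest on assumed means and SD.

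The size is minor. It concerns one biomarker outcome in HIV-positive participants, and the biomarker row states no power figure that could be upset. A reader should not conclude that the sample size, the stated minimum detectable effects or the suppression outcome are in doubt.

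**What to change.** - In Table 2, move viral load to the Continuous column as log10 viral load, with the base stated. Analyse it under the existing Gaussian identity-link mixed model, using the baseline value already collected.
- State one rule for values below 30 copies/mL. For example, set them to a fixed value in the Gaussian model and add a censored-regression sensitivity analysis. Left-censoring is not part of the Gaussian model that section 8.3 lists, so it has to be named separately. A baseline value below 30 needs the same rule, and so do provider results, whose detection limit section 6.6.3.3 does not give.
- Keep viral suppression as the dichotomous form, and leave the dried blood spot entry in the Count column.

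Cost: one table cell, one or two sentences and a small sensitivity analysis. No new data and no change to the sample size are needed.

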9.0 ANALYTIC APPROACH

9.1 Specific Aim 1a Analysis

Aim 1a, which begins the efficacy trial, is a two-arm, non-blinded RCT whereby half of all participants are randomly assigned to receive the Getting Off app immediately (ID arm; n=150; equivalent to an “active intervention” arm) and half are randomly assigned to receive the app after a 30-day delay (DD arm; n=150; equivalent to a “control” arm). The proposed analytical model allows for causal analysis of intervention effects. Power Calculations for Specific Aim 1a: estimated RCT MDEs for HIV Prevention or Care Continuum outcomes related to Specific Aim 1a are: 1) dichotomous (Di)—Odds Ratio (OR) = 1.97; 2) counted (Cu)—Incidence Rate Ratio (IRR) = 1.51; 3) continuous (Co)— f^2 = 0.03; for methamphetamine use outcomes: 1) Di—OR = 0.48; 2) Cu—IRR = 0.85; 3) Co— f^2 = 0.05; for HIV sexual risk behaviors outcomes: 1) Di—OR = 0.52; 2) Cu—IRR = 0.78; 3) Co— f^2 = 0.05.

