You'll have opportunities during this program to look at these areas of your life again so you can see the areas where you're making improvements and the areas you may need to focus more energy on.

Session 1: Calendars and Dots Around the Clock

Top left: Each user can personalize his avatar by choosing facial structure, skin tone, hair, facial hair, clothing, and background. Bottom left: An example of the translation from manual to app. Right: Screenshots showing how the *Getting Off* app provides information on the stages of recovery from methamphetamine use, a risk calculator for methamphetamine use and high-risk sexual behaviors, a reflective exercise on disassociating sexual behaviors from methamphetamine use, and a goal-setting exercise to increase self-efficacy.

A feasibility pilot test was conducted on the original eight sessions. Participants (N=15) in the feasibility pilot test were 40% Caucasian/White, 33% African American/Black, and 27% Hispanic/Latino; 73% identified as gay and 27% identified as bisexual. Ages ranged from 25-55 years (Mean=43; SD=9); 67% were HIV positive. Most (87%) met criteria for DSM-5 methamphetamine use disorder (60% severe). In the past 30 days, 80% reported methamphetamine use, 67% reported sex with a casual male partner (Mean=1.7; SD=0.9), and 25% reported sex with an anonymous male partner (Mean=2.5; SD=2.4). Pilot test participants were identified as similar to prospective app users; 53% (n=8) were out-of-treatment, current methamphetamine users and 47% (n=7) were methamphetamine users who had recently sought treatment for their methamphetamine use with no more than six months of recovery. Backend app user data indicated that average progression rates (i.e., how much of a session the participant completed) ranged from 62% (Recall) to 91% (Redefine), and the median completion rate for every session was 100% across all 15 participants. Twelve (80%) participants finished all sessions and completed both the initial and closing self-assessments; on average these participants reported improvements in self-esteem, social life, family life, drug

use, and alcohol use. Follow-up interviews (n=14; 93%) indicated mean participant satisfaction rating was high (8.5/10).

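### Aim 1a f-squared is 0.05 in section 9.1 but 0.03 in Table 2 for two outcomes, and the count IRRs rest on no stated mean, zero fraction or dispersion

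*Combined protocol and SAP*

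**What the plan says.** Section 9.1 lists the Aim 1a minimum detectable effects. For methamphetamine use, after the odds ratio, it gives "2) Cu—IRR = 0.85; 3) Co— f^2 = 0.05", and for sexual risk "2) Cu—IRR = 0.78; 3) Co— f^2 = 0.05". Table 2 (section 8.3), Model 1, same aim and same n=150/150, gives "Di: OR = 0.48; Cu: IRR = 0.85; Co: f^2 = 0.03" in the Substance Use Frequency row and "Di: OR = 0.52; Cu: IRR = 0.78; Co: f^2 = 0.03" in the BQA row. The Aim 1a odds ratios, the IRRs and the continuum f-squared (0.03) agree between the two places; only these two f-squared cells differ.

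For continuous outcomes, section 8.3 says the models "assume a single covariate unless otherwise stated". All calculations are for 80% power at two-sided 0.05.

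The stated inputs are probabilities. Section 8.2 says the continuum calculations "assume a 30% probability of achievement of at least one of the steps on either the HIV Prevention or Care Continuum" (about 1:2 odds) and the methamphetamine calculations "assume an 80% probability of methamphetamine use during the pre-intervention period for participants in the DD arm (equivalent to 4:1 odds of use"). Section 8.3 uses 65% (about 2:1 odds) for sexual risk. No mean, variance, dispersion or zero fraction is given for any count. Section 8.3 does foresee excess zeros and overdispersion, but only as a reason to change the analysis model.

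**The concern.** A minimum detectable effect should be a single number for a given aim, outcome and sample size. Two f-squared values for the same cell cannot both be the 80%-power value.

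For counts, a detectable rate ratio depends on the mean and the spread. A probability of any event, or its odds, does not fix either. Days of use and number of condomless anal intercourse episodes are listed count versions of primary outcomes, and the reader is told that the randomized comparison can detect reductions of 15% (IRR 0.85) and 22% (IRR 0.78) with 80% power. If that is optimistic, a null count result could be taken to exclude reductions of that size when it does not.

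**Working it through.** **1. f-squared, Aim 1a.** Inputs: N=300, one tested predictor (section 8.3), two-sided 0.05, 80% power. Method: F test with 1 and 298 degrees of freedom, noncentrality f² × N.

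- 80% power needs f² = 0.0263, which rounds to Table 2's 0.03.
- Power at f² = 0.05 is 97.1%.
- 0.05 would be the 80% value with about 160 participants in total (0.0497), or with 7 to 8 tested parameters at N=300 (0.0490 and 0.0514). The plan states neither.

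**2. Reproducing the count IRRs.** No mean is stated, so I tried the printed odds (0.5 continuum, 4 methamphetamine, 2 sexual risk) as plain Poisson means m. Wald test on log IRR: variance = 1/(n₀m) + 1/(n₁ × m × IRR), solved for |log IRR| = (1.96 + 0.84) × SE. Aim 1b is treated as two independent groups of 300.

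| Aim (n₀/n₁) | Continuum: computed (stated) | Methamphetamine | Sexual risk |
|---|---|---|---|
| 1a (150/150) | 1.517 (1.51) | 0.844 (0.85) | 0.783 (0.78) |
| 1b (300/300) | 1.352 (1.35) | 0.889 (0.89) | 0.844 (0.85) |
| 1c (600/300) | 1.294 (1.30) | 0.903 (0.90) | 0.863 (0.87) |

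All nine agree to within about 0.01. This is an inference about how they were obtained; the plan does not say so.

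**3. Consistency with the stated probabilities.** A Poisson count has P(any) = 1 − exp(−m). Means of 0.5, 4 and 2 give 39%, 98% and 86%, against the stated 30%, 80% and 65%. A count with those means and the stated zero fractions can exist, but it is overdispersed relative to Poisson.

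**4. Power at the stated Aim 1a IRRs if the stated probabilities are the non-zero fractions.** Let P0 be the fraction with zero (0.70, 0.20, 0.35) and c the coefficient of variation (CV) among those with any event. For the ratio of overall means, unadjusted, with the same P0 and c in both arms:

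- CV² of the whole count = (P0 + c²)/(1 − P0)
- variance of log IRR = 2 × CV²/150
- power = Φ(|log IRR|/SE − 1.96)

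*Methamphetamine, IRR 0.85.* At c=0, CV² = 0.20/0.80 = 0.25, SE = 0.0577, |log IRR| = 0.1625, ratio 2.81, power 80%. At c=0.25, CV² = 0.328, SE = 0.0661, power 69%. At c=0.5, 47%.

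*Sexual risk, IRR 0.78.* At c=0, CV² = 0.35/0.65 = 0.538, SE = 0.0847, |log IRR| = 0.2485, ratio 2.93, power 83%. At c=0.25, 77%. At c=0.5, 61%.

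*Continuum, IRR 1.51.* At c=0, CV² = 0.70/0.30 = 2.33, SE = 0.176, |log IRR| = 0.412, power 65%.

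If instead the whole effect works through the fraction with any event, with equal counts among them, variance = [(1−p)/p + (1−p × IRR)/(p × IRR)]/150. This gives 77% for the continuum (p from 0.30 to 0.453), 65% for methamphetamine and 70% for sexual risk. The better of the two routes is therefore about 77%, 80% and 83%.

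**5. Effect of baseline adjustment.** Multiply the variance by 1 − ρ², where ρ is an assumed baseline correlation. At ρ=0.5 and c=0.25, methamphetamine rises from 69% to 81% and sexual risk from 77% to 88%. At ρ=0.5 and c=0.5 they reach 58% and 73%.

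**The case against.** The strongest reply is that the power figures in step 4 are for an analysis the plan does not describe. It specifies mixed-effects models with outcome-related covariates and premises power on two time points, so some variance reduction is likely. This stands. With an assumed R² of 0.5, hurdle-type scenarios with the effect on the count reach about 72–93% (methamphetamine), 87–96% (sexual risk) and 80–89% (continuum). A rate ratio defined only among those who engage also does better: 91% for sexual risk at a CV of 0.53. But the plan states neither a baseline correlation nor which rate ratio is meant, so it cannot rely on either without saying so.

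A reader might infer that the trial is underpowered for its counts. The documents do not support that. Using 30/80/65% as non-zero fractions for the counts is itself a reading, and other listed counts, such as metabolite-free urine samples, need not follow it. If the probabilities are set aside, a larger mean with little overdispersion exceeds 80%.

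A reader might also take the pilot as proof of large spread: "67% reported sex with a casual male partner (Mean=1.7; SD=0.9), and 25% reported sex with an anonymous male partner (Mean=2.5; SD=2.4"). Those figures give CVs of 0.9/1.7 = 0.53 and 2.4/2.5 = 0.96, at which unadjusted sexual-risk power would be 59% and 34%. They are partner counts, not intercourse episodes, from a pilot of 15 men, and 25% of 15 is not a whole number. They are illustrative only, and nothing in the documents informs the spread of days of use.

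Finally, 0.05 might be read as a sign of reduced power. It is not: the trial has more than 80% power at that value.

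**Conclusion.** Two points hold. First, section 9.1 and Table 2 conflict on f-squared for methamphetamine use and sexual risk in Aim 1a. Under the single-covariate default 0.03 fits (exact value 0.026), and 0.05 is wrong as an 80%-power value. This is a reporting error with no loss of power.

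Second, the count IRRs are undocumented, and the only reading found that recovers them conflicts with the plan's own probabilities if those apply to the counts. On that condition and without adjustment, the claimed 80% is just reached for methamphetamine and slightly exceeded for sexual risk only when everyone with any event reports the same count. It is missed for the continuum by either route examined. Any appreciable spread lowers it further. Adjustment in the planned models could restore it, so a shortfall is possible but not shown. The CVs and correlations used here are assumptions. The dichotomous odds ratios are not affected.

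**What to change.** - **f-squared:** use 0.03 for the two outcomes in section 9.1, or state the number of tested parameters that gives 0.05 and change Table 2 to match.
- **Placement:** Table 2 prints the methamphetamine f-squared in a row whose continuous variable is N/A, although section 8.2 names the Treatment Effectiveness Score. Put the value with that score. The continuum f-squared also sits beside N/A, and section 8.2 defines no continuous version; define one or remove the value.
- **Counts:** recompute the IRRs in Table 2 and in the Aim 1a, 1b and 1c paragraphs of section 9 from a stated mean, zero fraction and dispersion consistent with 30/80/65%, using a negative binomial or zero-inflated model. Say whether the ratio is of overall means or among those with any event, state any assumed baseline correlation, and show the detectable IRR over a range of dispersion (for example CV 0.25 to 1.0 among those with any event). If the historical records for Aim 1c hold these counts, they could supply the inputs.

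The cost is a recalculation and edits to one table and three paragraphs, with no new participants or data collection. The downside is that the count effects may become less favourable. The odds ratios need no change on this ground.
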